- Mean MRSE at 4 months postoperative compared to target MRSE
- Percent of eyes with MRSE within 0.50 D and within 1.00 D of target MRSE at 4 months postoperative
- Contrast acuity at 4 months postoperative compared to 3-month.
- Mean change in total meibomian gland score from 3 months to 4 months postoperative.
- Mean change in total SPEED score from 3 months to 4 months postoperative.
- Rates of adverse events in the Study and Control groups.
- Rates of medical and/or lens findings in the Study and Control groups.

STUDY VISITS AND PROCEDURES:

Inclusion and exclusion qualifications will be assessed at the start of Preoperative Visit #1 according to the protocol criteria. The Informed Consent Document and Authorization for Use/Disclosure of Health Information form (HIPAA authorization) must be signed by any subjects who agree to participate in the study prior to undergoing any study-specific procedures. After determination that all inclusion/exclusion criteria have been met, enrolled subjects will be randomized to either Study group or Control group in a 1:1 ratio.

Study visit schedule, procedures and key data collected at each visit are shown in **Appendix A, Appendix B, and Section 10.2, Visit Schedule, Table 1.**

DATA ANALYSIS:

Key study endpoints are the comparisons between study group and control group for precision of biometric measurements preoperatively, mean change in total Meibomian gland score at 1 month postoperatively, mean monocular UCDVA at 3 months postoperatively, rate of refractive predictability at 3 months postoperatively and rate of directed reported ocular symptoms at 3 months postoperatively. Additional endpoints will be evaluated at 1 and 3 months postoperatively for the both groups and 4 months postoperatively for crossover Control group.

Visual acuity data will be converted to LogMAR values prior to analysis. Comparisons between study group and control group for the mean monocular UCDVA at 3 months postoperatively will be performed using one-sided two-sample t-tests with alpha set at 0.05. Precision of preoperative biometric measurements is defined as the average of the three computed standard deviations from each preoperative visit. The Study group is expected to have better total Meibomian gland score at 1 month postoperatively compared to the Control group, and to have better

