6.1 KEY STUDY ENDPOINTS

- MEAN MONOCULAR UCDVA AT 3 MONTHS POSTOPERATIVE IN THE STUDY AND CONTROL GROUPS
 - Success criteria: Statistically significantly lower mean LogMAR UCDVA is expected in the study group eyes compared to control group eyes at 3 months postoperative.
- PRECISION (STANDARD DEVIATION) OF PREOPERATIVE AL, ACD, AND KERATOMETRIC MEASUREMENTS (K) FOR THE STUDY AND THE CONTROL GROUP
 - AL, ACD and K values will have three sets of measurements at the Preoperative Visit #1 and again at the Preoperative Visit #2. For AL, ACD and keratometry, the standard deviation of each set of measurements will be computed at both preoperative visits, and the average of the three computed standard deviations from each preoperative visit is defined as the precision. The difference in precision between the two preoperative visits will be calculated for AL, ACD and K values. The precisions of the AL, ACD and keratometry measurements are expected to be better (smaller standard deviation) for study group eyes than the ones for control group eyes.
- RATE OF REFRACTIVE PREDICTABILITY AT 3 MONTHS POSTOPERATIVE FOR THE STUDY AND CONTROL GROUPS
 - The frequency, proportion and 95% confidence intervals of eyes with achieved MRSE within 0.50 D and 1.00 D of targeted MRSE will be summarized at 3 months postoperatively. The proportion of study group eyes with achieved MRSE within 0.50 D and within 1.00 D of targeted MRSE is expected to be greater compared to control group eyes.
- RATE OF BOTHERSOME OCULAR SYMPTOMS AT 3 MONTHS POSTOPERATIVE FOR THE STUDY AND CONTROL GROUPS
 - The rate of directed reports of bothersome ocular symptoms (halos, night glare, starburst, and night vision difficulties) at 3 months postoperatively is expected to be lower for study group eyes than that for control group eyes.

- MEAN CHANGE IN TOTAL MEIBOMIAN GLAND SCORE IN THE STUDY GROUP COMPARED TO THE CONTROL GROUP FROM BASELINE TO 1 MONTH POSTOPERATIVE
 - Change in total Meibomian gland score is defined as total Meibomian gland score at 1 month postoperative minus the score at Baseline (before LipiFlow treatment). Greater mean change in total Meibomian gland score is expected for study group eyes than that for control group eyes.

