20.1 ANALYSIS POPULATION

The primary study population will be all eyes that are randomized for precision of biometric measurements, and all eyes that are randomized and implanted for all other analyses. Mean change in total Meibomian gland score will be compared between study group eyes and control group eyes at 1 month postoperatively. All other key study endpoints will be evaluated at 3 months postoperatively. Additional endpoints will be evaluated at 1 month and 3 months postoperatively for the study group and control group and 4 months postoperatively for crossover control group only. Missing data will not be imputed.

Since both eyes of the same subject will be randomized into the same group, eye-specific measurements of same subject are clustered and likely to be positively correlated. As a subset analysis, right and left eyes of subjects will be analyzed for the key eye-specific study endpoints separately to assess for any differences by eye. Demographics/enrollment/accountability data and binocular data will be reported for all randomized subjects with study IOLs successfully implanted..

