20.2 KEY STUDY ENDPOINTS

- MEAN MONOCULAR UCDVA AT 3 MONTHS POSTOPERATIVE

The mean LogMAR monocular UCDVA will be reported for study group eyes and control group eyes. Note that a lower LogMAR value is a better acuity.

The success criterion is a statistically significantly lower mean LogMAR monocular UCDVA for study group eyes compared to control group eyes ($p \leq$

0.05) at 3 months postoperative. The right eyes and left eyes data from each group will also be presented.

- **PRECISION (STANDARD DEVIATION) OF PREOPERATIVE AL, ACD, AND KERATOMETRIC MEASUREMENTS (K)**

AL, ACD and K values will have three sets of measurements at the Preoperative Visit #1 and three sets of measurements at the Preoperative Visit #2. For AL, ACD and keratometry, the standard deviation of each set of measurements will be computed at both preoperative visits and the average of the three computed standard deviations from each preoperative visit is defined as the precision. The difference in precision between the two preoperative visits will be calculated for AL, ACD and K values. The precisions of the AL, ACD and keratometry measurements are expected to be better (smaller standard deviation) for study group eyes than the ones for control group eyes. The right eyes and left eyes data from each group will also be presented.

- **RATE OF REFRACTIVE PREDICTABILITY AT 3 MONTHS POSTOPERATIVE**

The frequency, proportion and 95% confidence intervals of eyes with achieved MRSE within 0.50 D and 1.00 D of targeted MRSE will be summarized at 3 months postoperatively. The proportion of study group eyes with achieved MRSE within 0.50D and within 1.00 D of targeted MRSE is expected to be greater compared to control group eyes. The right eyes and left eyes data from each group will also be presented.

- **RATE OF BOTHERSOME OCULAR SYMPTOMS AT 3 MONTHS POSTOPERATIVE**

The frequency and proportion of subjects who experienced moderate or severe ocular symptoms (halos, night glare, starburst, and night vision difficulties) will be reported. The rate of directed report bothersome ocular symptoms at 3 months postoperatively is expected to be lower for study group subjects than that for control group subjects.

- **MEAN CHANGE IN TOTAL MEIBOMIAN GLAND SCORE FROM BASELINE TO 1 MONTH POSTOPERATIVE**

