#### 2 ANALYSIS POPULATIONS

#### 2.1 ANALYSIS POPULATIONS

The primary analysis population will be all eyes that are randomized for the precision of biometric measurements, and all eyes that are randomized and implanted for all other analyses. Mean change in total Meibomian gland score will be compared between study group eyes and control group eyes at 1 month postoperatively. All other key study endpoints will be evaluated at 3 months postoperatively. Additional endpoints will be evaluated at 1 month and 3 months postoperatively for the study group and control group and 4 months postoperatively for crossover control group only. Missing data will not be imputed.

Since both eyes of the same subject will be randomized into the same group, eye-specific measurements of same subject are clustered and likely to be positively correlated. As a subset analysis, right and left eyes of subjects will be analyzed for the key eye-specific study endpoints separately to assess for any differences by eye. Demographics/enrollment/accountability data and binocular data will be reported for all randomized subjects with study IOLs successfully implanted.

Version 1.0 1 SAP/DRYE-102-SELF

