#### 4 STUDY ENDPOINTS

#### 4.1 KEY STUDY ENDPOINTS

#### 4.1.1 MEAN MONOCULAR UCDVA AT 3 MONTHS POSTOPERATIVE

The mean LogMAR monocular UCDVA will be reported for study group eyes and control group eyes. Note that a lower LogMAR value is a better acuity. The success criterion is a statistically significantly lower mean LogMAR monocular UCDVA for study group eyes compared to control group eyes ( $p \le 0.05$ ) at 3 months postoperative visit. The right eyes and left eyes data from each group will also be presented.

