#### **APPENDIX I: TABLE LISTING**

Variable	All Subjects	Study/control group	Note
ENROLLMENT/PREOP/OP			
Accountability/Enrollment			
Subjects/eyes by investigational site (n)	x	X	Subjects and eyes
Accountability table over time – (Available for analysis, Missing data –Forms not yet completed, Active, Missed visit, Lost to follow-up, Discontinued) (n and %)	Х	х	Subjects and eyes
Out of Interval listing	Х	Х	Subjects and eyes
Demographics			
Demographic – Age in years (N, Mean, SD, Min, Max), race, sex, ethnicity (n and %) Age in groups (<30, 30-39, 40-49, 50-59, 60-69, ≥70) (n, %)	х	х	Subjects
Preoperative Characteristics			
Target refraction (MRSE) - (N, Mean, SD, Min, Max)		x	eyes
BSCVA in groups (≤20/30, 20/40, 20/50-20/80, 20/100, >20/100) – (n,%)		х	eyes
Total Meibomian gland score at 1 st preop visit (baseline)- (N, Mean, SD, Min, Max, 95% CI)		х	eyes
Number of MGYLS at 1 st preop visit (baseline) – (N, Mean, SD, Min, Max, 95% CI)		x	eyes
TBUT at 1 st preop visit (baseline) – (N, Mean, SD, Min, Max, 95% CI)		x	eyes
SPEED score at 1 st preop visit (baseline) – (N, Mean, SD, Min, Max, 95% CI)		x	eyes
Eyelid margin evaluation assessment (obvious/minimal changes/normal appearance; Obvious/Non-obvious MGD) at 1st preop visit (baseline) – (n, %)		х	eyes
KEY STUDY ENDPOINTS			
Mean monocular UCDVA at 3-month (N, Mean, SD, Min, Max, 95% CI of LogMAR)		х	Eyes, also by right eye and left eye

Precision (avg. of SD from 3 sets of measurements) of preop (2 nd visit) AL, ACD and Ks	x	Eyes, also by right eye and left eye
Rate of MRSE predictability at 3-month (achieved MRSE within 0.5D/1.0D of target MRSE) – (n, %)	х	Eyes, also by right eye and left eye
Rate of bothersome ocular symptoms at 3-month – (n, %)	х	subjects
Mean change in total Meibomian gland score from baseline to 1- month – (N, Mean, SD, Min, Max, 95% CI)	х	Eyes, also by right eye and left eye
ENDPOINTS EVALUTED AT 1-MONTH POSTOP		
Mean change in number of MGYLS from baseline – (N, Mean, SD, Min, Max, 95% CI)	х	eyes
Mean change in ocular surface stain grade from baseline— (N, Mean, SD, Min, Max, 95% CI)	х	eyes
Mean change in TBUT from baseline- (N, Mean, SD, Min, Max, 95% CI)	х	eyes
Eyelid margin evaluation assessment (obvious/minimal changes/normal appearance; Obvious/Non-obvious MGD) at 1-month – (n, %)	х	eyes
ENDPOINTS EVALUTED AT 3-MONTH POSTOP		

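### Read as written, the UCDVA success test counts two correlated eyes per subject as independent, so its one-sided 5% error is really about 7.5% to 11% at assumed inter-eye correlations of 0.3 to 0.8

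*SAP*

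**What the plan says.** Protocol 20.1 and SAP 2.1 take as primary population, apart from biometric precision, "all eyes that are randomized and implanted for all other analyses". Both sections note that the two eyes of a subject share an arm, and both state that "eye-specific measurements of same subject are clustered and likely to be positively correlated". Their only response is this: "As a subset analysis, right and left eyes of subjects will be analyzed for the key eye-specific study endpoints separately". The stated purpose is to look for differences between eyes.

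Success on monocular UCDVA at 3 months is defined by eye throughout:

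- Protocol 6.1: "Statistically significantly lower mean LogMAR UCDVA is expected in the study group eyes compared to control group eyes at 3 months postoperative".
- Protocol 20.2, at p<=0.05: "statistically significantly lower mean LogMAR monocular UCDVA for study group eyes compared to control group eyes".
- SAP 4.1.1, at the same threshold: "The success criterion is a statistically significantly lower mean LogMAR monocular UCDVA for study group eyes compared to control group eyes".

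The UCDVA row of SAP Appendix I also gives eyes as the unit, with right and left eyes shown in addition.

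The Data Analysis part of the Protocol Synopsis says that the UCDVA comparisons "will be performed using one-sided two-sample t-tests with alpha set at 0.05". The sample size text (Protocol Synopsis and 20.5, SAP 5) assumes the same test, but with 55 subjects per group. SAP 4.1.1 names no test and no sidedness. Neither document mentions a mixed model, GEE, cluster-robust variance, subject average or designated primary eye.

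**The concern.** Randomization is by subject and the analysis is by eye. Two positively correlated eyes carry less information than two independent ones, so an ordinary t-test on all eyes understates the standard error of the difference between arms. The plan recognises the dependence and then makes no allowance for it in the analysis that decides success.

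UCDVA is the only endpoint with a stated alpha, so it carries the study's only formal success decision. If the test is run as the documents describe, that decision does not have the 5% error it claims. If the method is instead left open, the choice among all eyes, right eye, left eye and a clustered model would be made after the data are seen, in an open-label study.

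The eye-level 95% confidence intervals for UCDVA and gland score (SAP Appendix I) and for refractive predictability (SAP 4.1.3) have the same gap.

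**Working it through.** **Inputs from the documents.** One-sided two-sample t-test, alpha 0.05 (Protocol Synopsis). Difference 1 line, SD 1.6 lines, 55 subjects per group, 20% loss (SAP 5). Two eyes per subject in the same arm (SAP 2.1), so up to 110 eyes per arm.

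**Assumed.** Inter-eye correlation (ICC) of 0.3, 0.5 and 0.8; the documents give no value. The SD of 1.6 lines is taken as the per-eye SD.

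**The plan's own figure.** With n = 55 per group, d = 1/1.6 and one-sided alpha 0.05, power is 94.7% (noncentral t; 94.9% by the normal approximation). This agrees with the SAP's claim of more than 90%. The Protocol's plain 90% fits a two-sided 0.05 test (90.1%). Enrolment: 55/0.8 = 68.75, rounded up to 69, as stated.

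**Effect of ignoring the pairing.** With two eyes per subject in one arm, the variance of an arm mean is inflated by 1 + ICC. Hence:

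- true one-sided error = 1 - Phi(1.645/sqrt(1+ICC))
- coverage of a nominal 95% interval for a mean = 2*Phi(1.96/sqrt(1+ICC)) - 1
- ratio of correct to naive interval width = sqrt(1+ICC)
- effective number of eyes per arm = 110/(1+ICC)

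| ICC | 1.645/sqrt(1+ICC) | One-sided error | Simulated error | 95% CI coverage | Width ratio | Effective N |
|---|---|---|---|---|---|---|
| 0 | 1.645 | 5.0% | 4.9% | 95% | 1.00 | 110 |
| 0.3 | 1.443 | 7.5% | 7.4% | 91% | 1.14 | 85 |
| 0.5 | 1.343 | 9.0% | 9.0% | 89% | 1.22 | 73 |
| 0.8 | 1.226 | 11.0% | 11.2% | 86% | 1.34 | 61 |

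The simulation used 100,000 trials per row, normal data, 55 subjects (110 eyes) per arm and a pooled t-test on all eyes. The ceiling, at ICC = 1, is 1 - Phi(1.163) = 12.2%.

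**Analyses that respect the pairing.** In simulations of 40,000 trials at ICC 0.3, 0.5 and 0.8, a t-test on subject means rejects in 5.0%, 4.9% and 5.0% of trials. With 10% of subjects contributing one eye only, it rejects in 5.1%, 5.1% and 5.2%. A right-eye-only test rejects in 5.1%, 4.8% and 4.9%.

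**Power after correction.** The SD of a subject mean is 1.6*sqrt((1+ICC)/2) = 1.29, 1.39 and 1.52 lines. With 55 subjects per arm and a 1-line difference, one-sided power is about 99%, 98% and 96%.

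**Proportions.** For the refractive predictability intervals, assume a true proportion of 0.80 and an exact binomial interval on 110 eyes (the SAP names no interval method). Coverage is then 92.7%, 90.6% and 86.9%.

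**The case against.** The strongest reply is that the plan is silent rather than wrong. The Synopsis sentence naming the t-test compares groups and does not give eyes as the unit, and the sample size text counts subjects, as a subject-level analysis would. No sentence says the eyes are treated as independent. That is fair: the all-eyes t-test is an inference from several sections read together. But those that define the population, the success criterion and the table row all say eyes, and no section offers another analysis. If the plan is merely silent, the same correction is needed.

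Second, right-eye and left-eye results are pre-specified and would sit beside the all-eyes result. Each holds about 5%, so a reader could see whether success survives. This mitigates the problem without curing it, because no rule says what follows if the three results disagree.

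Third, sidedness matters. If p<=0.05 in SAP 4.1.1 means two-sided, total rejection is 8.6%, 11.0% and 14.4%, but false success in the favourable direction is half of that: 4.3%, 5.5% and 7.2%. These exceed their nominal 2.5%, yet pass 5% only when ICC is above about (1.96/1.645)^2 - 1 = 0.42. So the statement that any positive correlation takes the error above 5% belongs to the Protocol's one-sided test.

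Finally, the size rests on an assumed ICC. That stands. The direction and the 12.2% ceiling do not depend on it.

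**Conclusion.** The concern holds. Following the two documents as written gives a test whose one-sided error is about 7.5% to 11% instead of 5%, for an assumed inter-eye correlation of 0.3 to 0.8. Any positive correlation, which the sponsor itself expects, puts it above 5%. The error-rate statement is confined to UCDVA; for the other eye-level endpoints the consequence is confidence intervals that are too narrow. The defect concerns false-positive error, not sample size: effective N stays above the planned 55 per arm throughout the range. Because it affects the only formal success criterion, it must be corrected before the data are analysed.

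A separate and lesser point: SPEED gives one score per subject and SAP 4.2.2 compares subjects, but Protocol 20.3 and the baseline, 3-month and 4-month SPEED rows of SAP Appendix I refer to eyes. If each score were in fact entered once per eye (ICC = 1), intervals would have 1/sqrt(2) = 0.71 of the correct width and about 83% coverage. No section says this will be done, but the labels need to be reconciled.

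**What to change.** State in SAP 2.1 and 4.1.1, and in matching terms in the Protocol Synopsis (Data Analysis), 6.1 and 20.1-20.2, that UCDVA success is read from one named analysis that accounts for two eyes per subject, and give its sidedness. Any one of these would do:

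- a two-sample t-test on subject means, which is closest to the test the Synopsis already names;
- a mixed model with a random intercept for subject;
- GEE clustered on subject.

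If subject means are used, add a rule for subjects implanted in one eye only, whom Protocol 10.6 Note 3 foresees; for example, that eye's value stands for the subject.

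Use cluster-adjusted 95% confidence intervals for eye-level endpoints that report them, including the proportions within 0.50 D and 1.00 D. Label right-eye and left-eye results as supportive. Separately, set the SPEED wording in Protocol 20.3 and all SPEED rows of SAP Appendix I to subjects.

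The cost is wording and a few lines of code. Intervals for means become about 14%, 22% and 34% wider than the naive ones at ICC 0.3, 0.5 and 0.8, and p-values rise accordingly. No additional subjects or data are needed.

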#### 2.2 VISIT WINDOWS

Each randomized group will have two preoperative visits, 1 month postoperative visit and 3 months postoperative visit. Subjects randomized to study group will receive LipiFlow treatment before the second preoperative visit. Subjects randomized to control group will receive crossover LipiFlow treatment after 3 months postoperative visit. There will be a 4 months postoperative visit for control group subjects. The exact number of days for each interval is described in the protocol. The number of eyes with missing visits or data outside of the visit intervals will be reported.

#### 2.3 DATA CONVENTIONS

Descriptive statistics will typically include sample size (N), mean, standard deviation (SD), median, minimum (Min.), and maximum (Max.) as appropriate for continuous variables. 95% confidence interval around the mean will be reported where appropriate. For categorical data, the frequency and proportion will be computed.

For visual acuity data, letter scores will be converted to LogMAR prior to analysis. Formulas used for visual acuity analysis are included in Appendix II. For refractive data, all values will be converted to minus cylinder with sphere adjusted for infinity. Formulas used for refractive data are included in Appendix III.

#### 3 ACCOUNTABILITY/DEMOGRAPHICS

#### 3.1 ACCOUNTABILITY

The number of randomized subjects will be tabulated by site and by study group and control group. Subject accountability will be summarized as a frequency distribution by scheduled visits. The frequency and proportion of available subjects, including those outside of the interval, and the frequency and proportion of missing subjects (forms not yet completed, active, missed visit, lost to follow-up or discontinued) will be reported.

#### 3.2 DEMOGRAPHICS

Subject demographic data including age, sex, race and ethnicity will be presented by study group and control group. Age will be summarized with descriptive statistics with mean, standard deviation, minimum and maximum. In addition, age will be categorized by less than 30, 30 to 39, 40 to 49, 50 to 59, 60 to 69, 70 and older group. The frequency distributions of sex, race, ethnicity and age group will be tabulated.

Version 1.0 2 SAP/DRYE-102-SELF

#### 4 STUDY ENDPOINTS

#### 4.1 KEY STUDY ENDPOINTS

#### 4.1.1 MEAN MONOCULAR UCDVA AT 3 MONTHS POSTOPERATIVE

The mean LogMAR monocular UCDVA will be reported for study group eyes and control group eyes. Note that a lower LogMAR value is a better acuity. The success criterion is a statistically significantly lower mean LogMAR monocular UCDVA for study group eyes compared to control group eyes ( $p \le 0.05$ ) at 3 months postoperative visit. The right eyes and left eyes data from each group will also be presented.

### 4.1.2 PRECISION (STANDARD DEVIATION) OF PREOPERATIVE AXIAL LENGTH (AL), ANTERIOR CHAMBER DEPTH (ACD) AND KERATOMETRIC MEASUREMENTS (K)

AL, ACD and K values will have three sets of measurements at the preoperative visit #1 and three sets of measurements at the preoperative visit #2. The standard deviation of each set of AL, ACD and K values will be computed at both preoperative visits and the average of the three computed standard deviations from each preoperative visit is defined as the precision. The difference in precision between the two preoperative visits will be calculated for AL, ACD and K values. The summary statistics of the difference in precision of AL, ACD and K values will be reported for study group eyes and control group eyes. The precisions of the AL, ACD and K values are expected to be better (smaller standard deviation) for study group eyes than the ones for control group eyes. The right eyes and left eyes data from each group will also be presented.

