To evaluate the function of the meibomian glands, the Investigator or designee assesses the color and consistency of the secretion characteristics from the gland orifices along the lower eyelid. The Investigator or designee evaluates the glands using a slit-lamp biomicroscope and a handheld diagnostic instrument, Meibomian Gland Evaluator (MGE) (as shown in **Appendix G**), to apply gentle pressure along the eyelid margin, which simulates a forceful blink in yielding secretions from the glands. This instrument provides a standardized method to apply the same amount of pressure at each visit and for each subject to ensure measurement consistency. This Class I, 510(k)-exempt device is commercially available, and is being used in this study in accordance with the indications in the commercial product labeling.

There are approximately 20 to 30 meibomian glands along the lower eyelid. The Investigator or designee assesses and grades glands located temporally, centrally and nasally, as shown in **Appendix G**. The central region of the Meibomian Gland Evaluator should be carefully placed in the temporal, central and nasal regions as described in **Appendix G** to avoid overlap in the gland assessment.

VISUAL ACUITY TEST

The subject must be predictably capable of achieving Snellen 20/30 (Decimal 0.6) or better best corrected distance vision in each eye after cataract extraction and IOL implantation. The surgeon may use his/her judgment, the Potential Acuity Meter (PAM), or other methods (e.g., pinhole, laser interferometer, etc.) to estimate the subject's potential postoperative acuity.

Preoperative UCDVA and BCDVA tests should be performed per site standard of care.

MANIFEST REFRACTION AND REFRACTION ADJUSTMENTS

Preoperative manifest refraction is required. Preoperative refraction tests would be performed per site standard of care.

CORNEAL TOPOGRAPHY

In each designated preoperative visit, corneal topography measurements will be collected on both eyes. The instrument printouts and anonymized database export from the respective instruments will be collected from the site. No irregular corneal astigmatism should be present preoperatively.

KERATOMETRY AND BIOMETRY

In each designated preoperative visit, the investigator shall repeat 3 sets of biometry / keratometry measurements with at least 3 measurements in each set (depending on the measuring device).

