#### 1 INTRODUCTION

This document summarizes the statistical methods to be implemented during the analysis of data for the evaluation LipiFlow treatment in cataract surgery practice. This is a post-market, prospective, randomized, multi-center, bilateral, open-label, cross-over, comparative clinical study. Up to 140 subjects will be randomized and bilaterally implanted to achieve approximately 110 evaluable subjects (55 in the study arm and 55 in the control arm).

The purpose of this study is to evaluate the LipiFlow treatment in adult patients with mild to moderate Meibomian gland dysfunction (MGD) undergoing bilateral cataract surgery in terms of preoperative surgical planning and postoperative outcomes including refractive outcomes, visual outcomes and ocular comfort.

The key study endpoints are the comparisons between study group and control group for precision of biometric measurements preoperatively, mean change in total Meibomian gland score at 1 month postoperatively, mean monocular UCDVA at 3 months postoperatively, rate of refractive predictability at 3 months postoperatively and rate of bothersome ocular symptoms at 3 months postoperatively. Additional endpoints will be evaluated at 1 month and 3 months postoperatively for the both groups and 4 months postoperatively for crossover control group.

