#### 6 STUDY INTERIM REPORTS

An interim database lock will be performed for preoperative data after completion of the second preoperative visit.

Version 1.0 6 SAP/DRYE-102-SELF

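### Biometry precision is a visit 1-to-2 difference in SAP 4.1.2 but visit 2 only in SAP Appendix I; fix one headline analysis, adjusted for visit-1 precision and site, before the preoperative lock

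*SAP*

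**What the plan says.** Both documents define precision, at each preoperative visit, as the mean of three within-set standard deviations. The Protocol synopsis (Data Analysis) puts it as "Precision of preoperative biometric measurements is defined as the average of the three computed standard deviations from each preoperative visit", with no difference between visits.

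Protocol 6.1 and 20.2 add: "The difference in precision between the two preoperative visits will be calculated for AL, ACD and K values". They do not say that this difference is what the arms are compared on. SAP 4.1.2 goes one step further: "The summary statistics of the difference in precision of AL, ACD and K values will be reported", for study and control eyes.

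The key-endpoint row in SAP Appendix I reads: "Precision (avg. of SD from 3 sets of measurements) of preop (2 nd visit) AL, ACD and Ks". The appendix has no row for the difference and none for visit-1 precision. It does have first-visit baseline rows for gland score, MGYLS, TBUT and SPEED.

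Protocol 6.1, Protocol 20.2 and SAP 4.1.2 all state the expected benefit on the precisions themselves, without naming a visit or the change. SAP section 1 treats the endpoint as a between-group comparison: "The key study endpoints are the comparisons between study group and control group for precision of biometric measurements preoperatively". On timing, SAP section 6 says: "An interim database lock will be performed for preoperative data after completion of the second preoperative visit".

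**The concern.** Better biometric precision is the first item in the clinical hypothesis (Protocol section 3). For this key endpoint the SAP text and the SAP table listing call for different quantities, and neither document gives a test, a success criterion or an estimator of the arm difference. A programmer working from Appendix I would not produce the quantity that SAP 4.1.2 promises.

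The study is open-label and the preoperative data have their own interim lock. Two unranked versions of a key endpoint leave room to choose between them after the data have been seen. The two can differ in size, and sometimes in direction, on the same data.

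**Working it through.** **Inputs.** The plan has no power or variance figure for precision; its only sample-size statement concerns UCDVA (SAP section 5). The enrolment figure there reproduces: 55/(1 − 0.20) = 68.75, so 69 per arm. I use 69 because this endpoint's population is all randomised eyes (SAP 2.1). The visit-to-visit correlation r, the inter-eye correlation ρ and the SD of precision are not in the documents. I assume r = 0.3 to 0.7, ρ = 0 to 1 and, unless stated, equal spread at both visits. Change is taken as visit 2 minus visit 1.

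**1. Gap between the two versions.** Let D1 and D2 be the arm differences in mean precision at visits 1 and 2. Visit 2 only estimates D2; the change score estimates D2 − D1. The gap is −D1. Visit-1 biometry precedes LipiFlow (Protocol synopsis, Visit Schedule), so D1 is pure chance imbalance.

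SD of gap = √(2/n) × √((1+ρ)/2) eye-level SDs. For n = 69, √(2/69) = 0.170.

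| ρ | SD of gap | 95% range |
|---|---|---|
| 0 | 0.120 | ±0.24 |
| 0.5 | 0.147 | ±0.29 |
| 1 | 0.170 | ±0.33 |

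**2. Opposite directions.** With one value per subject, corr(D2, D2 − D1) = √((1−r)/2). With no true effect, the chance of opposite signs is arccos(√((1−r)/2))/π. At r = 0.5 this is arccos(0.5)/π = 0.33. The rows for a true effect come from bivariate normal simulation, with the effect in subject-mean SDs.

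| True effect | r = 0.3 | r = 0.5 | r = 0.7 |
|---|---|---|---|
| 0 | 30% | 33% | 37% |
| 0.2 SD | 16% | 16% | 14% |
| 0.3 SD | 8% | 6% | 5% |

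**3. Efficiency.** In units of the visit-2 variance, visit 2 only has variance 1, the change score 2(1−r), and the analysis adjusted for visit 1 has 1−r². The ratios to the adjusted analysis are therefore 2/(1+r) for change and 1/(1−r²) for visit 2 only.

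| r | Change / adjusted | Visit 2 only / adjusted |
|---|---|---|
| 0.3 | 1.54 | 1.10 |
| 0.5 | 1.33 | 1.33 |
| 0.7 | 1.18 | 1.96 |

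A simulation of the subject-mean analysis with 7 sites, allocation balanced within site, and site and baseline in the model (6000 runs) gave 1.55/1.29/1.16 and 1.09/1.35/1.88.

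If visit-2 spread is k times visit-1 spread, change/adjusted = (1 + k² − 2rk)/(k²(1−r²)). This is 2.40/2.15/2.04 at k = 0.7 and 1.24/1.10/1.01 at k = 1.3. Visit 2 only/adjusted does not change.

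**4. What r might be.** Protocol 10.3 asks sites to "repeat 3 sets of biometry / keratometry measurements with at least 3 measurements in each set", which is a minimum, not a fixed number. With the same lognormal true SD at both visits (CV 0.3), r is 0.47, 0.65 and 0.81 for 3, 5 and 10 readings per set. Neither unadjusted version is therefore safely the better one: visit 2 only wins below r = 0.5, and the change score wins above it.

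**The case against.** The best case for the plan has four parts.

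- **SAP 4.1.2 should govern.** It is the analysis text, its only group-reporting sentence names the difference, and the protocol calculates the same difference. The departure is one line in a table listing with other gaps: no baseline staining row, no confidence interval in the refractive-predictability row, and 4-month SPEED and gland-score rows labelled as change from baseline. This narrows the ambiguity. It does not remove it, because no precedence rule is stated and the tables are built from the listing.
- **The missing statistics are covered.** SAP 2.3 sets default summaries for continuous variables, so the bare precision row matters little. That is right. SAP 2.3 gives no estimator of an arm difference, however.
- **The lack of a test is general.** Only UCDVA has a success criterion and a sample size, so covariate adjustment is an improvement, not the cure for the contradiction. This is fair: stating one quantity in both places cures the contradiction without a model.
- **The opposite-direction rates look worse than they are.** With no true effect, either sign is noise. Opposite signs with at least one 95% interval excluding zero occur in under 2% of trials on the same assumptions, and opposite signs with both intervals excluding zero almost never. This also stands. The practical risk is a different estimate and a different reading of it, seldom two firm and contrary conclusions.

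**Conclusion.** The concern holds. The mismatch between SAP 4.1.2 and Appendix I is textual and depends on no assumption. The protocol does not resolve it, and the SAP change history records only a visual-acuity formula update.

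Its numerical consequence is moderate and rests on assumed inputs: a gap between versions with SD 0.12 to 0.17 eye-level SDs at 69 per arm. Relative to the adjusted analysis, the variance penalty over r = 0.3 to 0.7 with equal spread is 18% to 54% for the change score and 10% to 96% for visit 2 only. A higher r is possible, so these are not upper limits. No variance is given for site, so the gain from that term is not quantified; it is included because site is the randomisation stratum (Protocol 10.3).

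This should be corrected, but it does not threaten the trial's sizing or the UCDVA endpoint.

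**What to change.** Before the preoperative interim lock, put the same headline analysis in SAP 4.1.2 and Appendix I for each of AL, ACD and K:

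- Compare visit-2 precision between arms, adjusted for visit-1 precision and site, using the mean precision of the subject's two eyes at each visit. With visit-1 precision in the model, the arm effect is the same whether the outcome is visit 2 or the change, so one model serves both passages.
- Report the adjusted arm difference with a 95% CI, and state whether the scale is raw or log.
- State which keratometric value K means (Appendix I says Ks, and Protocol Appendix T records K1 and K2), and how a subject with one measured eye is handled.
- If an eye-level model with a random subject effect is preferred, include the subject-mean visit-1 value as well as the eye's own. In a deliberately extreme simulated structure, the model with only the eye's own baseline was less efficient than visit 2 alone (variance ratio visit 2/model 0.87), whereas subject-mean adjustment was not (1.09).
- Add Appendix I rows for visit 1, visit 2 and change as description, and keep the right-eye and left-eye presentations.

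If no model is wanted, the minimum is to name the same headline quantity in both places.

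The cost is SAP wording, a few table rows and one model per parameter. No new data are needed. The one drawback is that the headline becomes a model-adjusted difference instead of a raw mean.
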